11.2. Reporting of Adverse Events

The Investigator or designee will record all AEs while the Subject is enrolled in the clinical study. This includes AE that are device or study procedure related as well as those events with no relationship to the study. Examples include:

- Device related (ADE): insertion site infection
- Serious adverse device effect (SADE): cellulitis at device insertion site requiring hospitalization
- Procedure related AE: bruising at IV insertion site

Subjects participating in the study have diabetes and are expected to experience hypoglycemia and or hyperglycemia. These normal events are not expected to be reported to Sponsor on an AE eCRF as this is not considered an untoward event, but rather an expected occurrence. Any glycemc excursion that meets the protocol definition of Severe Hypoglycemia or DKA is considered an untoward event and a worsening from the subject's baseline and would be reported to Sponsor on an AE CRF.

Adverse events will be documented in the subject source file and reported to sponsor on an eCRF. The Investigational Center is responsible for documentation of AEs including obtaining source documents related to the event, such as emergency medical technician/paramedic reports, hospital records (admission summary; lab results, test results, discharge summary) or device uploads to support the event. Source documents will be reviewed to determine if additional AEs have occurred and require reporting.

Narratives gathered from completed questionnaires will not provide the basis of an AE report however could lead to discussions that result in the identification of a reportable AE.

Adverse events that have not resolved at the time of the subject's discontinuation or completion of the study should have an "outcome" of Not Recovered/Not Resolved at study end in subject source and on an eCRF. The Investigator should ensure that subject is aware of any follow-up or additional treatment that is required for any ongoing AE at end of study participation; however, there will be no eCRF entry for the ongoing follow-up.

11.3. Notification of Adverse Events

Sponsor Notification:

As soon as possible (desired within 24 hours) of investigator or study coordinator awareness, the Investigational Center staff must report all Severe Hypoglycemia; DKA; Serious Adverse Events; Serious Adverse Device Effects and any Unanticipated Adverse Device Effect to Medtronic. For the previously mentioned events, the AE eCRF will be completed with all known details details as soon as possible (desired within 24 hours) of Investigational Center awareness – this will serve as notification to Medtronic. If the study database cannot be accessed due to technical problems, contact the sponsor via email at [contact].

11.4. Expedited Safety Reporting Requirements

For device studies, investigators are required to submit a report of a UADE to the sponsor and the reviewing GCP office and EC as soon as possible after the investigator first learns of the event. Investigators are required to report these events details as soon as possible (desired within 24 hours) of awareness.

Documentation of GCP office and EC notification of any safety event must be kept at the Investigational Center and a copy sent to the sponsor.

It is the responsibility of the investigator to follow their EC reporting requirements.

Table 3. Investigator Reporting requirements for AE and Device Deficiencies

For the following events, reporting requirements are:
 
 • Serious Adverse Events (SAE) 	

Investigators shall immediately adopt appropriate therapeutic measures for subjects, and simultaneously report to the management department of medical device clinical study in Investigational Center in written form. Management department of medical device clinical study shall report to:
	
Medtronic	Immediately
Local food and drug regulatory authority and health and family planning competent authority of the province, autonomous region and municipality directly under the central government where the Investigational Center locates	Within 24 hours
EC	Within 24 hours/per EC's requirements

For the following events, reporting requirements are:
 
 • All other AEs • All other Device Deficiencies 	

Investigators shall record all the adverse events and device deficiencies occurred during the clinical study. Investigators shall analyze the reasons for the events with Medtronic and document the analysis result in written report, including the comments of continuing, suspending or terminating study, which shall be reported to the EC through management department of medical device clinical study in Investigational Center for review.
	
To Medtronic	Submit in a timely manner after the investigator first learns of the event.

CIP313 Clinical Investigation Plan

10688326DOC

Version B

Page 61 of 87

To EC	Per EC's requirements
For the following events, reporting requirements are: 
• Serious Adverse Events (SAE)• Device Deficiencies with SAE potential	
Medtronic submits to:	
The food and drug regulatory authorities and health and family planning competent authorities at the same level	Within 5 working days upon being informed
Other Investigational Center and investigators participating in the study	As per local reporting requirement
EC	Timely report to EC of the clinical Research institution through management department of medical device clinical study

NOTE: In case there is/are additional AE reporting requirement(s) and/or process(es) (e.g. internal hospital policy or province regulatory authority instruction, etc.), these specific AE reporting requirement and process must be documented in a separate cover.

11.5. Causality Assessment

An AE is not automatically related to the study device or procedure simply because the subject is wearing the device and participating in the study. The event should be reviewed to determine if the device or study procedure could have possibly caused the event and therefore is related to the study device or procedure.

Causality assessment is the determination of the relationship between an AE and the device being studied. A causal relationship is present if a determination is made that there is a reasonable possibility that the AE was caused by the study device or a study procedure. It is expected that the Investigational Center will review all elements surrounding the AE to properly assess the causality of the event to the study device or to a study procedure.

This review would include the subjects description of the event, study device uploads and medical records (if applicable) from the treating facility. These records will be made available to sponsor.

Investigators should classify the relationship between the AE and the study device or study procedures based on the five possible causality categories listed below:

- **Not related: relationship to the device or procedures can be excluded when:**
 - the event is not a known side effect of the product category the device belongs to or of similar devices and procedures
 - the event has no temporal relationship with the use of the investigational device or the procedures;
 - the serious event does not follow a known response pattern to the medical device (if the response pattern is previously known) and is biologically implausible;
 - the discontinuation of medical device application or the reduction of the level of activation/exposure - when clinically feasible – and reintroduction of its use (or increase of the level of activation/exposure), do not impact on the serious event;
 - the event involves a body-site or an organ not expected to be affected by the device or procedure;
 - the serious event can be attributed to another cause (e.g. an underlying or concurrent illness/ clinical condition, an effect of another device, drug, treatment or other risk factors);
 - the event does not depend on a false result given by the investigational device used for diagnosis, when applicable;
 - harms to the subject are not clearly due to use error;
 - In order to establish the non-relatedness, not all the criteria listed above might be met at the same time, depending on the type of device/procedures and the serious event.

- **Unlikely:** the relationship with the use of the device seems not relevant and/or the event can be reasonably explained by another cause, but additional information may be obtained.

- **Possible:** the relationship with the use of the investigational device is weak but cannot be ruled out completely. Alternative causes are also possible (e.g. an underlying or concurrent illness/

clinical condition or/and an effect of another device, drug or treatment). Cases were relatedness cannot be assessed or no information has been obtained should also be classified as possible.

- **Probable:** the relationship with the use of the investigational device seems relevant and/or the event cannot reasonably be explained by another cause, but additional information may be obtained.

- **Causal relationship:** the serious event is associated with the investigational device or with procedures beyond reasonable doubt when:
 - the event is a known side effect of the product category the device belongs to or of similar devices and procedures;
 - the event has a temporal relationship with investigational device use/application or procedures;
 - the event involves a body-site or organ that
 - the investigational device or procedures are applied to;
 - the investigational device or procedures have an effect on;
 - the serious event follows a known response pattern to the medical device (if the response pattern is previously known);
 - the discontinuation of medical device application (or reduction of the level of activation/exposure) and reintroduction of its use (or increase of the level of activation/exposure), impact on the serious event (when clinically feasible);
 - other possible causes (e.g. an underlying or concurrent illness/ clinical condition or/and an effect of another device, drug or treatment) have been adequately ruled out;
 - harm to the subject is due to error in use;
 - the event depends on a false result given by the investigational device used for diagnosis, when applicable;
 - In order to establish the relatedness, not all the criteria listed above might be met at the same time, depending on the type of device/procedures and the serious event.

11.6. Anticipated or Unanticipated

If the adverse event is determined to be related to the study device or study procedure the Investigator must then assess the event to determine if it is anticipated or unanticipated.

- **Anticipated:** the event is identified in the CIP; labeling; Investigator's Brochure or user guide.
- **Unanticipated:** the event has not been previously identified in the CIP; labeling; Investigator's Brochure or user guide.

11.7. Severity of Event

A clinical determination of the severity of the event will be made. The following guidelines should be used:

- **Mild:** transient, needing no special treatment, and/or does not interfere with the subject's daily activity.
- **Moderate:** low level of inconvenience or concern to the subject and may interfere with daily activities, but is usually improved by simple therapeutic remedy.
- **Severe*:** interrupts a subject's daily activity and typically requires intervening treatment.

*Please Note: In the classification of AEs, the term "**severe**" is not the same as "**serious**." The term "**severe**" relates to an indication of the intensity of a specific event (as in mild, moderate, or severe chest pain). The term "**serious**" relates to a participant/event outcome or action criteria, usually associated with events that pose a threat to a participant's life or functioning.

11.8. Skin Assessment: Glucose Sensor Insertion Sites

Skin irritation may be associated with the insertion procedure or device wear and may be associated with the adhesives and tapes used to secure the study devices. The area of skin associated with glucose sensor insertion & wear will be assessed following the removal of each glucose sensor by Investigational Center staff.

It is expected that subjects will experience mild irritation, redness, bleeding or bruising associated with the insertion and or wear of the glucose sensor and devices. These events are to be documented and captured on the Skin Assessment eCRF. An AE eCRF will only be completed if the skin assessment observation meets the following criteria:

- Infection
- Any observation that meets the criteria of moderate or severe classification per the skin assessment case report form (for example: bruising 8 cm in diameter; rash that requires prescription medication)

Subjects will not be required to return to the Investigational Center for examination to document resolution of Skin Assessment observations. The subject should be instructed to contact the Investigational Center for follow-up if there is any worsening or change that concerns the subject. Worsening should be assessed to determine if AE reporting is necessary.

11.9. Documentation of Symptoms During YSI FST

During YSI FST it is expected that subjects may experience minor symptoms that are related to the procedure requirement of driving glucose levels high and low. All symptoms experienced by the subject must be recorded on the appropriate log. Those symptoms that are minor and directly associated with the requirements of the FST would be recorded on the log only. Examples include:

- Headache
- Shakiness/tremors
- Discomfort associated with iv insertion

- Shortness of breath

Events that are more serious or those events which have an intensity of moderate or severe should be noted on the log and reported as AEs. This would include:

- Severe Hypoglycemia
- DKA
- Seizure
- Vomiting
- Chest pain
- Syncope/Fainting

12. Data Review Committees

A clinical events committee (CEC) consisting of external physicians with an expertise in Endocrinology and the management of diabetes including Insulin Pumps and CGM will be convened. The CEC will review all reports of:

- SAE
- SADE
- UADE
- Severe Hypoglycemia
- DKA

The CEC will assess these events to determine agreement or disagreement with the Investigator classification of the event. The sponsor will notify the Investigator of any disagreement in assessment of an event by the CEC.

13. Device Deficiencies and Troubleshooting

The subjects will be instructed to contact the Investigational Center staff with questions or concerns regarding study devices.

All device deficiencies (per definitions in table below) reported directly to the Investigational Center staff by a subject and those experienced by the Investigational Center staff will be reported on the appropriate eCRF.

Device Deficiency	Inadequacy of a medical device with respect to its identity, quality, durability, reliability, safety or performance. NOTE: Device deficiencies include malfunctions, use errors, and inadequate labeling. (ISO 14155:2011 section 3.15)
-------------------	---

	Any unreasonable risk caused by a medical device in normal use during clinical trial that may endanger human health or life safety, such as label error, quality issues, malfunction and etc. (CFDA Order No.25 Article 93)
--	--

Investigators shall record and report all the identified device deficiencies occurred during the study, analyze the reasons for the events jointly with sponsor, form written analysis report and propose the comments of continuing, suspending or terminating trials, which shall be reported to EC through management department of medical device clinical trials in investigational centers for review. See Table 3 for device deficiencies reporting requirements.

All device returns will follow the Return Sales Order (RSO) instructions. To return a study device as part of a device deficiency, the subject is to call the Investigational Center staff, and the Investigational Center is to contact sponsor.

It is the responsibility of the Investigator to follow their EC reporting requirements for device deficiencies.

14. Statistical Design and Methods

14.1. General Considerations

All data collected from the time of screening until the end of the study will be collected either on eCRFs or electronically by downloading the various devices. Data and analysis will be summarized in a Clinical Study Report.

14.2. Subject Disposition

The number of subjects enrolled in the study will be presented by study phase. The reasons for discontinuing prior to study completion will be summarized.

14.3. Sensor Disposition

The number of Enlite Sensor insertions and Enlite Sensor removals for every subject enrolled in the study will be presented.

A descriptive analysis of Enlite Sensor disposition including Enlite Sensor dislodgement and reasons why it dislodged will be included in the Final Report. Enlite Sensor insertion and removals will be characterized by the following:

- Enlite Sensor location
- Duration of Enlite Sensor wear by investigational center subject report
- The number and percentage of Enlite Sensors remaining in place at study end.
- Duration of Enlite Sensor wear (subject report) by insertion site.
- Reason for removal: for example, scheduled removal, AE, fell out.

The functional life of the Enlite Sensor will also be characterized. The duration of Enlite Sensor performance from the time of first valid Interstitial Signal (ISIG) to the last glucose reading (i.e., time to end of Enlite Sensor life) will be described with Kaplan-Meier curves.

14.4. Subject Demographics and Baseline Characteristics

Subject characteristics, including age, gender, race, ethnicity, medical diagnosis, height, weight, BMI, CGM experience, and baseline A1C will be summarized by descriptive statistics (mean, standard deviation, minimum, median, and maximum) for continuous variables and by counts and percentages for categorical variables.

14.5. Sample Size and Power

The sample size selected is based on the primary analysis of the primary effectiveness endpoint (i.e., accuracy), agreement in comparative readings of paired sensor and YSI glucose readings.

Based on previous study, using one sample T test (formula provided below) with a level of 0.975 (one sided), β of 0.8, μ_0 is 0.6, μ_α is 0.72 and σ is 0.32:

$$n = \sigma^2 \frac{(t_\alpha + t_\beta)^2}{(\mu_0 - \mu_\alpha)^2}$$

It is indicated that a sample size of 58 will have power greater than or equal to 80% to demonstrate that the overall agreement rate is greater than 0.6. Considering 20% drop out, we need to enroll 72 subjects.

14.6. Analysis Populations, handling of missing data, error

Data entry error or non-reasonable values will be cleaned before data analysis. No imputations will be done for missing data. All enrolled subjects who have at least one paired Enlite Sensor and YSI measurement will be included in the efficacy analysis population. All enrolled subjects who have a Enlite Sensor inserted will be included in the safety analysis population.

14.7. Assignment to Day of YSI FST

Adult subjects and subjects with age of 14 - 21 will be required to attend 7-hour sessions of frequent sampling in which agreement between YSI and Enlite Sensors connected to the iPro2 will be evaluated.

14.8. General Considerations for Data Analysis

14.8.1. Data Collection

Primary endpoint, secondary endpoints, and other descriptive endpoints will be based on retrospective data collected from primary sensor. Precision analysis will be based on data collected from both sensors.

14.8.2. Pairing Scheme

All YSI and fingerstick values collected will be presented. , Most of descriptive analyses will include all YSI values, such as those less than (<) 40 mg/dL, or greater than (>) 400 mg/dL as long as Enlite Sensor values are greater than or equal to (\geq) 40 mg/dL or less than or equal to (\leq) 400 mg/dL (displayed to users as Low or High without numerical numbers). Reference glucose values (YSI values or fingerstick values) will be paired with the closest Enlite Sensor value between [0, 5) minutes. The primary Enlite Sensor will be used as a reference for precision analysis. Clarke EGA will be restricted to YSI values of 40-400 mg/dL. The same pairing scheme will be utilized.

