9.2.6. Visit 5: End of Study

- Subjects will return to the clinic to remove their study devices
- Investigational Center staff will review documentation of time they calculated for T=145 hours where the sensor may be removed at that time or after that time to ensure that the devices are not removed pre-maturely
- Investigational center staff will address questions or concerns from subjects
- Investigational center staff will ask subjects about the occurrence of any AEs or device deficiencies.
- Investigational center staff will:

- Download the iPro2 data from CareLink iPro following completion of the study devices wear
- Obtain subject's Study Meter BG values and enter into CareLink iPro
- Collect subject's Patient Log Sheet
- Provide iPro2 data to sponsor
- Investigational center staff will perform a Skin assessment on the area of each of the Enlite Sensor insertion sites and document in subject source and complete the Skin Assessment eCRFs
- Investigational center staff will collect returned devices (See Table 1 in Device Accountability section) and unused supplies from subjects
- Subjects will complete a questionnaire about their Enlite Sensor experience.
- Primary sensor and secondary sensor will be randomly assigned via RDC.
- An Exit eCRF will be completed at this visit.

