9.4. Randomization and Treatment Assignment

Investigational Centers will receive this randomization assignment generated electronically in the study database from Medtronic. The first randomization scheme assigns the subjects to one of the following sensor wear days (Day 1, 3-4, or 6) which determines when they will be participating in the in-clinic YSI FST.

Once subject is assigned to the study group, subjects will stay in that randomization group during the study.

In addition, at the end of the study (Visit 5), another randomization scheme will be done to assign the primary and secondary sensor for each subject.

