14.12.5. Other Accuracy Analyses

The ARE, the absolute differences between the sensor and YSI relative to the YSI reference will be calculated for each day separately. Summary statistics will include its mean, standard deviation, min, median, and max.

The mean numerical bias, which is the difference between the sensor and YSI values, will be calculated for each day. Summary statistics will include its mean, standard deviation, min, median, and max.

Bland-Altman plots, with 95% CI, will be provided for each of the 3 study days. The paired differences between the sensor and YSI rating will be plotted against the X-axis reference of mean YSI and sensor values.

Descriptive subgroup analysis of Enlite Sensor performance (20% mean agreement rate (± 20 mg/dL (1.1 mmol/L) when Reference BG less than or equal to (\leq) 80 mg/dL (4.4 mmol/L))) will be performed in the following cohorts:

- **FST:**
 - Day 1
 - Day 3-4
 - Day 6

All analysis follow the definitions provided in: Performance Metrics for Continuous Interstitial Glucose Monitoring: Approved Guideline, CLSI POCT05-A [Klonoff et al. 2008].

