6.6.2 Pairing Scheme

(1) All YSI and fingerstick values collected will be presented. Most of descriptive analyses will include all YSI values, such as those less than ($<$) 40 mg/dL, or greater than ($>$) 400 mg/dL as long as Enlite Sensor values are greater than or equal to (\geq) 40 mg/dL or less than or equal to (\leq) 400 mg/dL (displayed to users as Low or High without numerical numbers).

Reference glucose values (YSI values or fingerstick values) will be paired with the closest Enlite Sensor value between [0, 5) minutes.

(2) The primary Enlite Sensor will be used as a reference for precision analysis. Reference glucose values (primary Enlite Sensor) will be paired with the closest Enlite Sensor value between [0, 5) minutes

(3) Clarke EGA will be restricted to YSI values of 40-400 mg/dL. The same pairing scheme will be utilized.

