7.2 Subject Demographics and Baseline Characteristics

Subject demographics and characteristics, including age, gender, race, ethnicity, medical diagnosis, height, weight, BMI, Type of diabetes, diabetes history, pregnancy test, baseline Hct and baseline A1C will be summarized by descriptive statistics (mean, standard deviation, minimum, median, and maximum) for continuous variables and by counts and percentages for categorical variables.

$$\text{Age} = (\text{Informed Consent Date} - \text{Date of Birth}) / 365.25;$$

$$\text{BMI} = \text{Weight (kg)} / (\text{Height (m)})^2.$$

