7.9 Other Descriptive Endpoints

- Data from the home-use portion will be described. Analysis will include but not be limited to: 20% mean agreement rate (± 20 mg/dL (1.1 mmol/L) when Reference BG less than or equal to (\leq) 80 mg/dL (4.4 mmol/L)) for all fingersticks (capillary SMBG) collected, Clarke Error Grid Analysis (EGA), Consensus Error Grid analysis, Absolute Relative Difference (ARD), bias, correlation between Enlite Sensor and fingersticks (capillary SMBG), and Bland-Altman plots. In addition, 20% mean agreement rate (± 20 mg/dL (1.1 mmol/L) when Reference BG less than or equal to (\leq) 80 mg/dL (4.4 mmol/L)) will be described by the subgroups mentioned below: frequent sampling. The number of actual calibrations performed per day by study subjects will be tabulated and presented.
- Similar descriptive subgroup analysis of Enlite Sensor performance with YSI in all devices will be performed.
 - **FST:**
 - Day 1
 - Day 3-4
 - Day 6
- Precision analysis: ARD, bias, and 20% mean agreement rate (± 20 mg/dL (1.1 mmol/L) when Reference BG less than or equal to (\leq) 80 mg/dL (4.4 mmol/L)) will be performed.

This part of indicators will be summarized by descriptive statistics. The analysis method will be referred to section 7.2.

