7.9.4 Precision Analysis

Precision analysis will be performed for the two sensors worn by the same subject in the same location. This part of indicators will be summarized by descriptive statistics. The analysis method will be referred to section 7.2.

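### The mean signed bias in the precision analysis is measured against a randomly labelled sensor, so its expectation is zero under a 1:1 draw and it says nothing about precision

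*Protocol*

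**What the plan says.** Protocol section 6 has each subject wear two Enlite sensors, each with its own recorder. Protocol 9.2.6 (Visit 5, when the devices come off) says: "Primary sensor and secondary sensor will be randomly assigned via RDC". Protocol 9.4 describes this as a second randomization: "another randomization scheme will be done to assign the primary and secondary sensor for each subject". Neither document gives the allocation ratio.

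The label then fixes the reference for precision. Protocol 14.8.2 says: "The primary Enlite Sensor will be used as a reference for precision analysis". SAP 6.6.2 repeats this and adds the pairing: "Reference glucose values (primary Enlite Sensor) will be paired with the closest Enlite Sensor value between [0, 5) minutes". The planned measures are in Protocol 5.2.3 and SAP 7.9: "Precision analysis: ARD, bias, and 20% mean agreement rate".

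Bias between two sensors has no definition of its own. The only definition, in Protocol 14.12.5 and again in SAP 7.9.5, is for sensor against YSI: "The mean numerical bias, which is the difference between the sensor and YSI values, will be calculated for each day". For the precision summaries, SAP 7.9.4 says: "This part of indicators will be summarized by descriptive statistics. The analysis method will be referred to section 7.2". SAP 7.2 calls for mean, SD, minimum, median and maximum.

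**The concern.** Bias is meaningful against YSI because YSI is an independent reference. In the precision analysis the reference is one of two interchangeable devices, picked by a draw after wear has ended. Random labelling is a sound way to choose which sensor enters the accuracy analysis, but it does not turn that sensor into a standard. The sign of secondary minus primary is random, so positive and negative differences cancel in expectation whether the sensors agree closely or badly. At stake is whether one of the three listed precision measures answers the precision question. A systematic difference between the two sensors, if there were one, would also cancel in the mean.

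**Working it through.** Neither document states a figure for the precision analysis, so there is none to reproduce.

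**Inputs.** About 60 completers (Protocol section 6); primary label random per subject (Protocol 9.4); bias as a signed difference (Protocol 14.12.5). Assumed: probability p = 0.5 that a given sensor is primary. The sizes of disagreement below, and the glucose distribution in the simulations, are also assumptions.

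**Expectation.** Let D be the signed difference between a subject's two physical sensors in a fixed order, and p the probability that the first of them is labelled primary. Then

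E[secondary − primary] = (2p − 1) × E[D].

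At p = 0.5 this is 0 for any D.

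**Spread over the draw.** If the two sensors differ by a constant D in each of n subjects, each subject contributes +D or −D at random, so the SD of the mean is D/√n.
- D = 40, n = 60: 40/√60 = 5.2 mg/dL.
- D = 20, n = 60: 20/√60 = 2.6 mg/dL.

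**Simulation, 1:1 labels, no fixed direction of difference** (60 subjects, 300 pairs each, 400 repeats, readings limited to 40–400 mg/dL):

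| Between-subject SD of the sensor difference (mg/dL) | Expected mean bias | SD of the study mean | SD of paired differences | ARD | 20% agreement |
|---|---|---|---|---|---|
| 10 | −0.1 | 1.3 | 14 | 8% | 94% |
| 40 | −0.1 | 4.8 | 41 | 25% | 55% |
| 80 | +0.4 | 10.5 | 77 | 53% | 31% |

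Mean bias stays at zero within simulation error. The other columns move as they should.

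**Systematic offset.** True offsets of 20 and 40 mg/dL give a mean of 19.9 and 39.9 when the sensors are ordered by a fixed attribute, and −0.2 in both cases under random labels.

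**Unequal draw.** For a 20 mg/dL offset, the formula gives (2 × 0.6 − 1) × 20 = 4.0 at p = 0.6 and (2 × 0.667 − 1) × 20 = 6.7 at p = 0.667 (simulated: 3.9 and 6.6). Both are far below 20.

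**Effect of the label on ARD and agreement, single pair.**
- Readings of 150 and 100 mg/dL: ARD is 50/100 = 50% or 50/150 = 33%, depending on the label; with the pair mean it is 50/125 = 40%.
- Readings of 100 and 122: 22/100 = 22% fails the 20% rule, 22/122 = 18% passes.
- Readings of 78 and 98: the 20 mg/dL difference passes the ±20 mg/dL rule if 78 is the reference, but 20/98 = 20.4% fails if 98 is.

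**Same effect at study level** (60 subjects, 300 pairs each, data held fixed and only the labels redrawn). With ARD near 11%, 19% and 27%, the SD of ARD over the draw is about 0.1, 0.4 and 1.1 percentage points. The agreement rate moves by about 0.5 to 0.6 points. ARD with the pair mean as denominator is 10.5%, 18.1% and 25.8%, against 10.6%, 18.5% and 27.1% with the primary reading. The dependence is small, but grows as the sensors diverge.

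**The case against.** The strongest reply is that this is one uninformative statistic in a descriptive analysis that otherwise works. SAP 7.2 also requires SD, minimum and maximum. With a constant 40 mg/dL difference, the bias table would show an SD of about 40 and a range from −40 to +40, beside a large ARD and low agreement, so nobody reading the whole table would miss it. This stands, and it limits the point to the centre of the bias distribution. The median is also symmetric about zero over the draw, so its sign means nothing, although in that example it can land on +40 or −40 rather than near zero.

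A second reply is that zero expectation needs a 1:1 ratio and a mg/dL definition, and neither is stated for this analysis. This also stands as a condition. Escaping the mg/dL condition does not rescue the measure: as a percentage of the primary reading, the mean is pushed upward by the random denominator. For 150 and 100 mg/dL the two possible values average (50% − 33.3%)/2 = +8.3% with no direction of difference at all.

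Three stronger readings are tempting. A reader might infer that a near-zero bias would be presented as proof of precision; no passage gives bias an acceptance limit or a role in any conclusion. A reader might infer that ARD and agreement are arbitrary too; that holds for single pairs, but the study-level effect is small. A reader might infer that a left–right difference is being hidden and could be recovered from existing data. Protocol 9.2.4.1 only says sensors may go on the left and right sides, the precision sections describe the two sensors as in the same location, and although sensor location is a disposition item (Protocol 14.3, SAP 7.3), no passage says that side is recorded for each sensor.

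**Conclusion.** The point holds for the mean signed bias. Under a 1:1 draw and a mg/dL definition it is expected to be zero whatever the disagreement. The observed mean will still scatter around zero: SD 5.2 mg/dL over the draw for a constant 40 mg/dL difference in 60 subjects, 2.6 for 20. The 1:1 ratio is the natural reading of a random assignment between two sensors; a moderately unequal draw would still show only a fraction of a systematic offset. The documents do not support the wider conclusion that the precision analysis as a whole fails. Success is judged on the primary endpoint alone (Protocol 14.9), so this is a minor improvement to a descriptive result.

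**What to change.** In SAP 6.6.2, 7.9 and 7.9.4:
- Drop the mean signed bias as a precision measure.
- Report the mean absolute paired difference, the paired ARD with the mean of the two sensors as denominator, and the within-pair SD or CV. None of these depends on which sensor is called primary.
- If 20% agreement is kept, applying the 80 mg/dL cut-off and the 20% limit to the pair mean removes its small label dependence as well.
- Report a signed difference only by a fixed attribute such as abdominal side, and only if that attribute is recorded for each sensor. Confirm this against the case report form first.

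The pair-mean measures use data already collected. The cost is a few lines of SAP text and minor reprogramming of the precision tables. SAP 7.13 should list the change, because the protocol also names bias and the primary-sensor reference.
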